#### **3.1.2 Statistical considerations**

##### *Time points*

There are three time points in this study, pre-randomisation, 3-5 months post-randomisation and 9-12 months post randomisation. Deviation of measurement of the planned post-intervention timepoint will be summarised and reported by treatment group. Data will be collected within a six-week window of the planned time-point (i.e. 6 weeks prior to group start date, 6 weeks post group end date, 6 weeks from 6-months post group ending)

##### *Stratification and clustering*

Randomisation was stratified by covariates: online or in person preference and currently receiving mental health treatment. These will be included as co-variates in the analysis. As the intervention occurs in groups, a group effect is possible and the model will include group as a co-variate to account for clustering within group.

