#### **1.1 Principal research objectives to be addressed**

The aim of this study is to examine the feasibility of trial methods and treatment acceptability to inform the planning and conduct of a definitive randomised controlled trial of BaP-Enjoying Family Life. The specific objectives are:

1. To assess (a) the primary feasibility parameters for participant recruitment and retention and (b) secondary parameters for BaP-Enjoying Family Life acceptability and fidelity.
2. To examine the acceptability of proposed trial methods, including randomisation.
3. To investigate the influence of participant and service factors on trial methods, intervention acceptability and fidelity, including in-depth qualitative analysis of interviews from a sub-group of participants to develop a fine grain understanding of parents/caregivers' subjective experience of trial and intervention procedures.
4. To obtain variance estimates for parents/caregiver and child outcomes for future sample size calculations.

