## **2.3 Adherence to allocated treatment and treatment fidelity**

Compliance with treatment will be described in terms of number of group sessions attended in each trial arm. The reasons for withdrawal from treatment or non-attendance where available will be summarised. The mean number of sessions attended will be compared across arms. The baseline demographic characteristics of those in each attendance group (Low attenders (<5 sessions), high attenders (5 or more) and non-attenders) will be compared in each trial arm and any statistically significant patterns reported.

Treatment fidelity will be summarised by trial arm. Checklists measuring fidelity developed for both arms will be completed by Parent Group facilitators together after each session. Fidelity to session content and delivery is scored from 0-2 (0=no, 1= not sure, 2= yes) across four items (content, time management, facilitation methods, delivery). Fidelity will be reported as a total score (out of 80 for EFL groups and 72 for BAP) and percentage for each group in each arm. Any missed content identified in the fidelity measure will be reported.

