### **3.2 Preliminary estimation of treatment differences**

The aim of analysis of treatment differences is to give an indication of the potential range of effect sizes from BaP-EFL compared to standard BaP. Analyses will estimate the difference in mean outcomes between patients randomised to BAP-EFL and EPEC-BAP following an intention-to-treat principle (i.e. all data from randomised participant will be included in analysis, regardless of attendance). Group difference estimates (i.e. change from baseline) and associated 95% confidence intervals will be reported comparing BaP-EFL and EPEC-BaP across T2 and T3. Cohen's d will indicate size of effect. Inferential statistics and p-values will not be reported and estimates obtained will not be used to claim strong evidence for the effectiveness or ineffectiveness of the intervention as the trial is not powered to detect differences between arms.

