#### **3.2.1 Analysis of primary and secondary outcomes**

No inferential statistics will be conducted on primary or secondary clinical outcomes, instead descriptive statistics will estimate the likely range of treatment effects (by reporting means and standard deviation) at post-treatment and 6-month follow up. Cohen's d and 95% CIs will be reported. For the primary clinical outcome of child behaviour, proportions of children scoring above the clinical cut off of  $\geq 131$  for the Intensity Scale and  $\geq 15$  for the problem scale will be reported at each time point. Mean difference in change from baseline, and 95% confidence intervals will be reported for all outcomes and subscales, but no comparison of treatment effect will be carried out.

Population variances for future power calculation will be determined using the upper 80th percentile of confidence intervals around the estimated population variance, as recommended by Browne (1995).

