#### *Model assumption checks*

The models assume normally distributed outcomes; this will have been checked when describing the data and if substantial departures from normality occur, transformations will be considered. Residuals will be plotted to check for normality and inspected for outliers.

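### Therapy group is entered as a covariate although every group sits in one arm, so on the plain reading the adjusted arm difference is not identified

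*SAP*

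**What the plan says.** Under 3.1.2, Stratification and clustering, the SAP names the two minimisation factors (online or in-person preference, current mental health treatment) and says of them: "These will be included as co-variates in the analysis". It then notes that a group effect is possible and that "the model will include group as a co-variate to account for clustering within group". It names no random effect, mixed model, cluster-robust standard error or ICC.

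Section 2.3 reports fidelity as a score and "percentage for each group in each arm", with different maxima for the two programmes: "Fidelity will be reported as a total score (out of 80 for EFL groups and 72 for BAP".

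Section 3.2 sets the target: "Analyses will estimate the difference in mean outcomes between patients randomised to BAP-EFL and EPEC-BAP", with 95% CIs at T2 and T3 and Cohen's d. Section 3.2.1 again promises mean differences in change with 95% CIs, "but no comparison of treatment effect will be carried out". That a model is fitted is confirmed under Model assumption checks: "The models assume normally distributed outcomes".

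Objective 4 in section 1.1 is "To obtain variance estimates for parents/caregiver and child outcomes for future sample size calculations". The SAP does not give the number or size of the groups.

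**The concern.** Group here means the parenting group, because the sentence is introduced by the fact that the intervention is delivered in groups. It is added in the same terms as the two minimisation factors, which are ordinary fixed covariates. A fixed term for every group uses up all the information on differences between groups. The arm difference is one of those differences, so nothing is left from which to estimate it.

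The promised adjusted difference and its CI would then be either undefined or a comparison of whichever two groups the software kept as references. The second outcome is worse, because a number appears and nothing marks it as arbitrary. The absence of p-values does not help: an estimate with a confidence interval also needs an identified coefficient.

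A second issue concerns objective 4. The SAP accepts that outcomes may cluster by group, yet plans no estimate of the between-group variance or ICC and does not say which variance will be carried to the definitive trial.

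**Working it through.** **The plan's own figure.** The SAP gives no figure on clustering. Its one precision figure, ±10.7 points for a 70% follow-up rate with n = 72 (1.4), reproduces: 1.96 × √(0.70 × 0.30 / 71) = 10.66 points (10.59 with 72 as divisor). It does not depend on the clustering model.

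**Step 1: nesting.** Four fidelity items scored 0 to 2 give 8 points per session, so 80/8 = 10 sessions for EFL groups and 72/8 = 9 for BAP groups. A group runs one programme and belongs to one arm.

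**Step 2: identification.** Let G_k be 1 for members of group k and 0 otherwise. For every participant, arm = the sum of G_k over the BaP-EFL groups. Arm therefore adds no column that the group indicators do not already span. Rank check with N = 72 (intercept, baseline, mental health treatment, delivery preference, group dummies, arm):

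| Groups (assumed) | Columns | Rank without arm | Rank with arm |
|---|---|---|---|
| 6 | 10 | 9 | 9 |
| 8 | 12 | 11 | 11 |
| 12 | 16 | 15 | 15 |

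If preference coincides with the mode in which a group is run, one further column is lost.

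**Step 3: what software may print.** In one simulated data set (8 groups of 9, ICC 0.10), the arm coefficient from a pseudo-inverse fit moved from 0.22 to 1.07 when only the reference group changed. A random intercept for group gave 0.73 (SE 0.29); ignoring clustering gave 0.73 (SE 0.23). Entering group as a numeric code gave 1.47, which depends on the numbering. This was not run in SPSS or R.

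**Step 4: size in an assumed layout.** Assume 8 groups of 9, 4 per arm, full follow-up and total variance 1. Dropping aliased columns in order leaves arm as one group mean minus another.

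- SE, in units of the within-group SD: √(2/9) = 0.471, against √(2/36) = 0.236 for 36 versus 36.
- The model takes the variance as 2(1 − ICC)/9. As an estimate of the arm effect, the contrast has variance 2[ICC + (1 − ICC)/9].
- ICC 0.05: SE ratio √(0.1056/0.1556) = 0.824. The interval reaches 1.998 × 0.824 = 1.646 true SEs, and coverage on 64 df is 89.5%.
- ICC 0.10: ratio √(0.100/0.200) = 0.707, reach 1.413, coverage 83.7%.
- Simulations gave 88.6 to 89.8% and 84.5 to 84.9%. Group means compared with t on 6 df kept about 95%.

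95% half-widths at ICC 0.05:

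- aliased contrast: 1.998 × √(2 × 0.95/9) = 0.92 SD
- group means: 2.447 × √(2 × 0.1556/4) = 0.68 SD
- clustering ignored: 1.994 × 0.236 = 0.47 SD

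**Step 5: variance for the definitive trial (same layout).** The residual of a fixed-group model estimates 1 − ICC: 0.95 at ICC 0.05 and 0.90 at 0.10. The raw within-arm variance has expectation (1 − ICC) + ICC × 36 × 0.75/35: 0.989 and 0.977. The design effect for groups of 9, 1 + 8 × ICC, is 1.08, 1.40 and 1.80 at ICC 0.01, 0.05 and 0.10.

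**Step 6: precision of an ICC from this trial.** With an observed ICC of 0.05, F = 1 + 9 × 0.05/0.95 = 1.474 on 6 and 64 df. The upper limit uses 1.474 × 4.952 = 7.30, so ICC = (7.30 − 1)/(7.30 + 8) = 0.41. The lower limit is negative and is set to 0.

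**The case against.** *The SAP never says fixed, and a random intercept would serve the stated purpose.* True: with a random intercept the arm effect is estimable. But the text gives group the same role as two ordinary covariates and mentions no random effect. An analyst who follows it literally fits the model that fails, so the sentence needs replacing.

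*The reported numbers may not come from this model.* Section 3.2.1 speaks of descriptive statistics and disclaims a treatment comparison; raw differences in change, their CIs and Cohen's d need no covariate model. This stands in part. The SAP does not tie the contrast to the model explicitly, but it describes a model with covariates and residual checks, and the group difference is the only estimand to which they could apply. The passages need reconciling.

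*The figures rest on an assumed layout.* This stands. The SAP gives no number of groups, group size or ICC, and it anticipates about 70% follow-up rather than 72 complete cases. Only the lack of identification is independent of the layout.

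*A reader might infer that the plan strips between-group variance out of the estimates meant for the definitive trial.* The document does not support that. Section 3.2.1 places those variances beside raw means and SDs and never ties them to a model residual; raw within-arm SDs keep most of the between-group component. The loss occurs only if the variance is taken from the fixed-group residual. Nor does the SAP say that the later sample size will ignore clustering.

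*Nothing important depends on it.* No progression criterion in Table 1 uses an arm effect, and section 3.2 disclaims claims of effectiveness. This stands and limits the severity.

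**Conclusion.** The sentence is wrong as written and should be fixed before analysis. With group as a fixed categorical covariate and groups nested in arms, the adjusted arm difference and its 95% CI are not identified, for any number of groups. This rests on the plain reading of the covariate wording and on the nesting shown by section 2.3.

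The size of the harm if a number is printed anyway is illustrative: under the assumed 8 groups of 9, SE 0.47 SD and coverage of about 89.5% and 84% at ICC 0.05 and 0.10. It would be too strong to read these as properties of the trial, or to say that its feasibility conclusions are at risk.

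On objective 4 the supported criticism is narrower: the source of the variance is not stated, and no between-group variance or ICC is planned although a group effect is acknowledged.

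**What to change.** Replace the sentence on group in 3.1.2 with wording such as:

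> Outcomes will be analysed in a linear mixed model with arm and the two minimisation factors as fixed effects and parenting group as a random intercept nested within arm, using Satterthwaite or Kenward-Roger degrees of freedom. If the model does not converge, group means will be compared between arms with t on (number of groups − 2) degrees of freedom.

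In addition:

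- State in 3.2 and 3.2.1 that the differences and 95% CIs come from this model, and reconcile this with the statement in 3.2.1 that treatment effects will not be compared.
- For objective 4, state that the variance is the total within-arm variance (between-group plus within-group), not the residual of a model with fixed group terms.
- Report the between-group variance and the ICC with its 95% CI. Note that with few groups it will be very imprecise (0 to 0.41 in the example above) and cannot alone set the definitive sample size.

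The cost is SAP wording and a standard model call in R or SPSS, with no new data. Intervals will be wider than in an analysis that ignores clustering but, in the assumed layout, narrower than those of the aliased contrast (half-width 0.68 against 0.92 SD at ICC 0.05).

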##### *Missing items in scales and subscales*

The number (%) with complete data will be reported. Where available the missing value guidance provided by authors of scales will be used. In it's absence, scales will be pro-rated for an individual if 20% or fewer items are missing. For example, in a scale with 10 items, pro-rating will be applied to individuals with 2 or less items missing. The average value for the 8 or more complete items will be calculated for

that individual and used to replace the missing values. The scale score will be calculated based on the complete values and these replacements.

#### *Missing baseline data*

Missing baseline data should not be an issue for the primary analysis as individuals were not randomised and offered the group if they did not complete baseline assessments.

#### *Missing outcome data*

No inferential statistics will be conducted. Correlational analysis will assess whether attendance correlates with missing outcome data. T-tests will be used to compare number of missing outcomes in intervention and control arms. If there is missing outcome data, we will investigate to see if any baseline variables are predictors of outcome missingness. Such variables could then be included as covariates in the model if deemed suitable for adjustment.

#### *Method for handling multiple comparisons*

This study is underpowered to report significance test, therefore no correction for multiple comparison need be applied.

#### *Method for handling non-compliance (per protocol/CACE analyses)*

In addition to the primary intention-to-treat analysis, the effect of actually receiving treatment as defined in the protocol will also be estimated. Per-protocol analysis will be conducted on participants who completed 5 or more sessions. Demographic factors and descriptive statistics for clinical outcomes will be reported for the per-protocol analysis. Results from the per-protocol analysis will be considered secondary to results of the primary analysis.

#### *Model assumption checks*

The models assume normally distributed outcomes; this will have been checked when describing the data and if substantial departures from normality occur, transformations will be considered. Residuals will be plotted to check for normality and inspected for outliers.

### **3.1.3 Sensitivity analyses**

None planned.

### **3.1.4 Planned subgroup analyses**

None planned

### **3.2 Exploratory analyses**

None planned.

### **3.3 Exploratory mediator and moderator analysis**

None planned.

### **3.4 Interim analysis**

None planned.

## **4. Software**

Data management: Data will be collected in Qualtrics and saved in SPSS database. Analyses will be performed in SPSS and R. Excel may be used for the production of graphs.

## B) QUALITATIVE ANALYSIS PLAN

### 5. Aims of qualitative analysis

In feasibility studies, process evaluation are important in the ongoing refinement and development of both the intervention and trial design prior to a full RCT through evaluating trial and intervention acceptability and identifying potential barriers to research and treatment participation. The Qualitative data and analysis collected form part of a nested process evaluation which seeks to develop a fine grain understanding of the participant's experience of trial methods, intervention acceptability and implementation to inform further development and modifications to both the trial and intervention.

Key areas of uncertainty the qualitative interviews aims to address are:

- Trial implementation and acceptability (*Qualitative semi-structured interview, structured intervention records*)
- Intervention acceptability (*Qualitative semi-structured interview, parent-report questionnaires*)
- Intervention impact and implementation (*Qualitative semi-structured interview, fidelity and structured intervention records*)

#### 5.1. Specific research questions

- 1) Trial implementation:
  - a. What were participant's experiences of the engagement and recruitment processes used?
  - b. What helped to engage and recruit participants with the research project?
  - c. What did participants experience as barriers and facilitators to completing data collection?
  - d. How do participants experience and understand the research procedures, including randomisation?
- 2) Intervention acceptability: How acceptable is the intervention to parents?
  - a. What were participants experience of the intervention content?
  - b. What were participants experience of the delivery factors e.g. peer-led, timing of activities?
  - c. What were the areas of meaningful change for parents as a result of the intervention?
  - d. How did the intervention meet or not meet parents needs?
- 3) Intervention impact and implementation
  - a. What barriers did parents experience to attending intervention?
  - b. Were there commonalities in the strategies reported which may help improve attendance?
  - c. What were the areas of commonality and difference between the experience of parents receiving online vs. in person groups?
  - d. What were parents experience of positive recruitment strategies to parenting groups?

### Data Analysis plan

#### 6.1 Sample

A purposive sample of 24 parent participants from both intervention and control arms of the trial to semi-structured interview. Purposive sampling will occur to recruit equal proportions of participants based on attendance and trial arm.

## 6.2. Data collection

Semi-structured interviews using topic guides will be audio-recorded. Interviews will be transcribed using a transcription service. A semi-naturalistic approach (e.g. including stutters, pauses, laughter) to transcription will be taken to ensure language reflects the participants real world (Oliver et al., 2005). The researcher will review transcripts alongside audio recording during familiarisation and clarify any mistakes in transcription

Data will be analysed using Nvivo software.

## 6.3. Analysis approach:

The Reflexive thematic analysis will follow an adapted version of the six phases laid out by Braun and Clark (2006, 2019; see Table 1). Thematic analysis will be inductive, aiming to represent patterns in participant's experiences. All data will be coded, and all codes will be noted. Analysis will also be semantic, with data organized to show patterns in semantic content and then interpreted. Themes will be presented and discussed with PhD supervisors and intervention stakeholders (e.g. PGLs, parents with significant emotional and interpersonal difficulties) throughout analysis, especially during phase 4-6.

**Table 1. Thematic analysis phases (adapted from Braun & Clark, 2006)**

| Phase          | Description  |
|----------------|--|
| Phase 1 | Familiarization with the data through re-reading and free coding the interview transcripts   |
| Phase 2 | Transcription will be checked against the tapes for accuracy.
Line-by-line coding of each transcript
Each data item will be given equal attention; surrounding data and question asked will be kept to give context to codes   |
| Phase 3 | Generation of themes from the line-by-line coding
An interactive processes using mind-maps and/or tables will be used to think about relationship between codes and themes.   |
| Phase 4 | Reviewing of themes in comparison with the coded extracts
Internal homogeneity and external heterogeneity will be checked to establish whether data within themes cohere together meaningfully and are demarcated from other themes. This will be done at 2 levels: 1) all codes and extracts will be reviewed and consider whether they form a coherent pattern and 2) each individual themes validity in relation to the data set will be considered. |
| Phase 5 | Refining and organization of themes into an internally consistent structure.
The essence of each theme and the aspects of the data captured will be identified and fitted into a broader overall story.   |
| Phase 6 | Writing of interpretation and thematic framework into a coherent results section
This phase involves going beyond the description to make an argument in relation to the research questions.  |

## 6.4. Ontological and epistemology positioning

A critical realist epistemology will inform analysis, with the researcher considering the data at the empirical level (as reported by the participant) whilst also being critical of the influence of the participants and researcher's implicit ideology and the interaction between the interviewer and interviewee on the construction of experience (Fletcher, 2017). Data analysis will occur iteratively alongside data collection to allow the

researcher to explore emergent themes with participants, whilst also maintaining flexibility and adherence to original interview schedules.

## 6.5. Reflexivity

The research coordinator will carry out semi-structured interviews and analyse the data. The research coordinator is a female white British PhD student in her mid-twenties with no children. She has previous experience working clinically supporting individuals with complex PTSD. She has interests in trauma, adversity and how this impacts development, and strongly believes in the importance of understanding an individual's behaviours, thoughts and affect in the context of their past and current experiences. She is critical of diagnostic frameworks and medical models of treatment.

She was heavily involved in study design and selection of measures in collaboration with the chief and co-investigators, and solely responsible for recruitment and data collection, meaning she has built relationships with the participants interviewed. She also edited and developed the Being a Parent-Enjoying Family Life manual. The researcher's motivation to develop and improve support for parents experiencing significant emotional is in line with the research aims. The researcher will keep reflective records throughout interviewing and data analysis to record thoughts, feelings and concerns which come up during the process.

